2 STUDY OBJECTIVES

Primary Objective

- To evaluate the anti-cancer activity of CDX-011 in metastatic, GPNMB over-expressing, triple-negative breast cancer as measured by the duration of progression-free survival (PFS).

Secondary Objectives

- To further assess the anti-cancer activity of CDX-011 in metastatic, GPNMB over-expressing, triple-negative breast cancer, as assessed by the objective response rate (ORR), duration of response (DOR), and overall survival (OS).
- To further characterize the safety of CDX-011 in metastatic, GPNMB over-expressing, triple-negative breast cancer.
- To obtain pharmacokinetic parameters and to explore the relationship between patient-specific measures of exposure and safety and activity parameters.

Exploratory Objective

- To assess whether treatment with CDX-011 is associated with improvement in quality of life and/or cancer-related pain as reflected by reduced analgesic use.

3 ANALYSIS ENDPOINTS

3.1 Primary Endpoint

- Progression-free survival (PFS)

3.2 Secondary Endpoints

The following secondary efficacy endpoints will be evaluated:

- Objective response rate (ORR)
- Duration of response (DOR)
- Overall survival (OS)

3.3 Exploratory Endpoints

- Quality of life as measured by EORTC-QLQ-C30 and/or cancer-related pain as reflected by reduced analgesic use

3.4 Safety Endpoints

The following safety-related endpoints will be evaluated:

- Incidence of adverse events
- Deaths on study
- Discontinuations of study treatment due to adverse events
- Hematology, chemistry, and other laboratory parameters
- Vital sign parameters
- Electrocardiogram (ECG) parameters

4 RANDOMIZATION AND BLINDING

4.1 Randomization

Eligible patients will be centrally randomized in a 2:1 ratio to receive CDX-011 or capecitabine. For subjects enrolled in the study under protocol amendments 3 and 4, the randomization will be stratified by the following factors:

- 0-1 prior line of chemotherapy for advanced disease vs. 2 prior lines of chemotherapy for advanced disease
- Progression-free interval ≤ 6 months after receipt of taxane therapy vs. progression-free interval > 6 months after receipt of taxane therapy
- Received anthracycline therapy previously vs. no prior anthracycline therapy

There are no subjects enrolled under the original protocol. In protocol amendments 1 and 2, different stratification factors are considered. Specifically,

- Strata Under Amendment 1:
 - No lines of prior chemotherapy for advanced disease vs. 1 line prior chemotherapy for advanced disease – 0 vs. 1
 - “Resistant” to anthracycline therapy (i.e., progression-free interval of ≤ 6 months after completing treatment) vs. “Exposed” to anthracycline therapy (i.e., progression-free interval of > 6 months after completing treatment).

- Strata Under Amendment 2 and 2.1:
 - 0-1 prior line of chemotherapy for advanced disease vs. 2 prior lines of chemotherapy for advanced disease
 - “Resistant” to anthracycline therapy (i.e., progression-free interval of ≤ 6 months after completing treatment) vs. “Exposed” to anthracycline therapy (i.e., progression-free interval of > 6 months after completing treatment).

In the stratified analysis for this study, the stratification factors in Amendment 3 will be used. Given the changes in protocol amendments in stratification factors, the primary analysis of efficacy will be based on the actual stratification factors that are corrected after randomization. In addition, the secondary analysis using the *stratification factors as randomized* will also be performed, with the following mapping approach:

- All patients randomized under Amendment 1 will be considered as 0-1 prior line of chemotherapy for advanced disease.
- All patients randomized under Amendment 1 and 2.1 will be considered as received anthracycline therapy previously.
- For all patients randomized under Amendment 1 and 2.1, their Progression-free interval after receipt of taxane therapy will be determined based on the actual data reported in the clinical database.
- All patients randomized under/after Amendment 3 use the final stratification factors in randomization.

4.2 Blinding

This is an open-label study; therefore, neither the patients nor the investigators will be blinded to study treatment. Radiological and clinical disease assessments will be reviewed centrally in a blinded manner by the independent review committee (IRC). Members of the IRC will be blinded to study treatment. For data integrity consideration, a blinding process was established and specified in the document of *CDX011-04 Blinding and Unblinding Procedures*. In brief, two biostatistical groups are established: a blinded team (Celldex biostatistics team responsible for execution of the Statistical Analysis Plan, day-to-day interactions with the study team, and final study analyses) and an unblinded team (PPD biostatistics team responsible for supporting the Data Monitoring Committee (DMC) meetings). The blinded team will not have access to randomization and treatment data, and the unblinded team will have full access to the database.

5 SAMPLE SIZE CALCULATION

The primary efficacy endpoint is progression free survival (PFS). For patients with metastatic advanced GPNMB-expressing breast cancer in the treatment setting under investigation, median PFS of 4 months is anticipated following randomization to capecitabine. It is hypothesized that CDX-011 will increase median PFS in such patients by 2.25 months (i.e., 4.0 vs 6.25 months). Under the assumption of proportional hazards, such an increase corresponds to a hypothesized hazard ratio of 0.64. If this hypothesized hazard ratio is true, 203 PFS events (total of two arms) determined by IRC will provide 85% power with 2-sided type I error of 0.05. Under the assumption of exponential distribution for each arm and uniform enrollment over 2 years, and 10% drop out rate (PFS events cannot be observed), 300 patients (200 in the CDX-011 arm and 100 in the capecitabine arm) are needed, and it is anticipated that 203 PFS events will be observed in approximately 26 months from the date the first patient is randomized. The sample size calculation is performed using SAS v9.4.

6 ANALYSIS POPULATIONS

6.1 Efficacy Analysis

6.1.1 Intent-to-Treat (ITT) Population

The Intent-to-Treat (ITT) population will include all patients who are randomized. Patients will be analyzed according to the treatment arm to which they are randomized (CDX-011 or capecitabine).

6.1.2 Per-Protocol Population

The Per-Protocol population excludes patients that may substantially affect the results of the primary analysis, due to important deviations from the protocol. The final determination on protocol violations, and thereby the composition of the Per-Protocol population, will be documented in a separate memo prior to locking the clinical database and final analysis. Patients in the Per-Protocol population will be included in the treatment arm to which they actually received.

6.2 Safety Population

The safety population will include all patients who receive at least one dose of study treatment (either CDX-011 or capecitabine). Patients will be analyzed according to the treatment which they have actually received (CDX-011 or capecitabine). A baseline measurement and at least one laboratory, vital sign, or other safety-related measurement

obtained after at least one dose of study treatment may be required for inclusion in the analysis of a specific safety parameter.

7 GLOSSARY/ANALYTIC DEFINITIONS

7.1 Study Treatment

The term “study treatment” represents CDX-011 or capecitabine.

7.2 Study Day 1

Study Day 1 corresponds to the date of the first dose of study treatment.

7.3 Study Day

Study Day represents the elapsed number of days from Study Day 1, inclusive.

Study Day $n = (\text{Date of assessment} - \text{Date of Study Day 1}) + 1$ day,

if Date of assessment \geq Date of Study Day 1. Or,

Study Day $n = (\text{Date of assessment} - \text{Date of Study Day 1}),$

if Date of assessment $<$ Date of Study Day 1. Unless otherwise specified, the timing of all study-related events, assessments, and interventions will be calculated relative to Study Day 1. Study Day -1 will be the day before Study Day 1, and in general, negative days will be measured backwards starting from Study Day -1 .

7.4 Cycle 1 Day 1

The first 21-day treatment cycle will begin with the first dose of study treatment, and will be denoted as “Cycle 1 Day 1”. In general, the start date of each cycle (i.e., Day 1 of Cycle k , where $k=1$ to maximum number of cycles started) equals the date of the first dose of study treatment administered in the corresponding cycle. If study treatment is permanently discontinued, then the cycle number and cycle day for study-related assessments done after the last cycle of dosing will be replaced in the tables, figures, and listings with the visit name (e.g., End of Treatment Visit, Disease Assessment Visit WK24). The visit date and study day also will be used to identify the timing of such assessments.

7.5 Cycle k Day j

Day j represents the elapsed number of days since the first dose of study treatment in Cycle k .

$$\text{Day } j = (\text{Date of assessment} - \text{Date of Day 1 in Cycle } k) + 1$$

Unless otherwise specified, the timing of study-related visits and assessments will be calculated relative to Day 1 in each cycle.

7.6 Baseline

Unless specified otherwise, the baseline values will be those values measured closest to but not after the first dose of study treatment on Day 1 of Cycle 1.

8 PATIENT INFORMATION

8.1 Patient Disposition

The number of patients who are included in ITT, Per-Protocol, and Safety will be summarized by treatment arm. The reason for exclusion from one or more analysis populations will be provided.

The number of patients who are in the treatment phase and post-treatment follow-up phase of the study will be summarized by treatment arm. Patients discontinuing from study treatment and the primary reason for discontinuation will be summarized by treatment arm. Patients who withdrew from study and with the primary reason for discontinuation will be summarized in a similar manner.

8.2 Demographics and Baseline Characteristics

The following demographic and baseline characteristics considered pertinent to the outcomes for patients with metastatic breast cancer will be summarized for ITT population:

- Age, age group (≤ 40 , $41 - 64$, ≥ 65), sex, race, ethnicity, region, height, weight, body surface area (BSA), body mass index (BMI), ECOG performance status
- Breast cancer history, including time since initial diagnosis, time since diagnosis of advanced and/or metastatic breast cancer, number of prior relapses, stage at initial diagnosis, any prior CNS involvement, histopathology, estrogen receptor (ER) status at initial diagnosis and for advanced/metastatic disease, progesterone

receptor (PR) status at initial diagnosis and for advanced/metastatic disease, HER2 receptor status at initial diagnosis and for advanced/metastatic disease, ER/PR combined status for advanced/metastatic disease, ER/PR/HER2 combined status advanced/metastatic disease, GPNMB expression level in tissue used for study eligibility, current sites of disease including visceral involvement, number of organs involved (1, 2, >=3)

- Breast cancer treatment history, including prior surgery and use of radiation, number of prior lines of anticancer therapies, and setting received, and for specific, therapies of interest; number of prior lines of treatment for advanced disease; received prior anthracycline (Y/N), and progression-free interval after receipt of taxane therapy (≤ 6 months, >6 month)

The medical history term will be assigned standardized terms using the Medical Dictionary for Regulatory Activities (MedDRA). It will be summarized based on the number and percentage of patients by MedDRA dictionary terms and will also be presented in data listings.

9 PRIOR AND CONCOMITANT MEDICATIONS

Prior and concomitant medications will be coded to the World Health Organization (WHO) drug generic term using the WHO Drug Dictionary. Prior medications are defined as medications that started before the first dose of study drug. Concomitant medications are defined as medications that (1) started before the first dose of study drug and continued after first dose, or (2) started on or after the first dose of study drug and within 28 days after last dose. Prior and concomitant medications will be summarized by Anatomical Therapeutic Chemical (ATC) classification therapeutic subgroup and WHO generic term. All medication data will be listed individually and summarized by treatment arm according to anatomical therapeutic class and generic name.

10 EFFICACY ANALYSES

10.1 Multiplicity Consideration

This study has no planned interim analysis. For the primary analysis of PFS at final analysis, the test will be performed at two-sided 5% significance level. For multiplicity adjustment consideration for secondary endpoints, when the primary PFS analysis is positive, to strongly control the type I error at 5% level, Hochberg procedure ([Hochberg 1988](#)) will be used for ORR and OS. Specifically, [Table 2](#) below describes the statistical testing scenarios:

**Table 2: Hochberg testing procedure of the secondary endpoints
ORR and OS**

P values	Reject
$P_{(2)} \leq 0.05$	$H_{(1)}$ and $H_{(2)}$
$P_{(1)} \leq 0.025$ and $P_{(2)} > 0.05$	$H_{(1)}$
$P_{(1)} > 0.025$ and $P_{(2)} > 0.05$	None

Note: $P_{(1)}$ and $P_{(2)}$ are ordered P values of two tests for $H_{(1)}$ and $H_{(2)}$ respectively such that $P_{(1)} \leq P_{(2)}$, where $H_{(1)}$ and $H_{(2)}$ are two tests for ORR and OS.

According to this procedure, ORR and OS will both be considered positive if each analysis yields a P value of ≤ 0.05 . Alternatively, any analysis resulting in a P value > 0.05 will not be considered positive. If only one analysis results in a P value > 0.05 , the other must yield a P value ≤ 0.025 to be considered positive.

DOR will be analyzed as descriptive only and the statistical testing is not planned.

The HRQOL for this study is considered exploratory. The primary measure of HRQOL is the global health status score based on the EORTC QLQ-C30 questionnaire. No adjustment will be made for HRQOL analyses, and the p-values will be evaluated in an exploratory manner using a nominal significance level 0.05 (2-sided).

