10.4 Objective Response Rate (ORR)

ORR will be estimated based on the proportion of patients in each treatment arm with measurable disease at baseline whose best overall response during the course of study treatment is complete response (CR) or partial response (PR). Tumor response will be assessed using RECIST 1.1. The primary analysis of ORR will be based upon evaluations by the IRC regardless of tumor response (CR or PR) confirmation. The secondary analysis of ORR will be based on the confirmed (no sooner than 28 days later) tumor response (CR or PR). Supplemental analysis will be performed based on investigator's review.

Exact 95% confidence intervals of ORR will be calculated by treatment arm using Clopper-Pearson method. The inferential comparison of the observed ORRs will be made using the Cochran-Mantel-Haenszel Chi-square test, stratified by the randomization stratification factors.

Subgroup analyses will be performed for the list of subgroups specified in [Section 10.2](#). Waterfall plots will be used to depict graphically for individual patients their maximum percentage shrinkage from baseline in the sum of the longest diameters in target lesions.

Best overall response will be classified as 'not evaluable / unknown' for patients with early progression or early death. Early progression will include patients who discontinue study treatment due to worsening disease but without objective evidence of disease progression, and their best overall response cannot be determined because tumor assessments were either incomplete or were never performed or not repeated. Similarly, early death will include patients who die without objective evidence of disease

progression beforehand, and their best overall response cannot be determined because tumor assessments were either incomplete or were never performed or not repeated.

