10.6 Overall Survival (OS)

OS is defined as the time from randomization to the date of death due to any cause. Patients who are alive or lost to follow-up as of the data analysis cutoff date will be censored at last known alive date before cutoff.

The OS will be summarized descriptively using the Kaplan-Meier method. Median follow-up for OS will be estimated according to the Kaplan-Meier estimate of potential follow-up ([Schemper 1996](#)). The KM plot will be produced by treatment arm.

The primary inferential comparison of this endpoint will use the stratified log-rank statistic to test the null hypothesis that the distribution of OS times is equal for the 2 treatment arms.

Subgroup analyses will be performed for the subgroup factors listed in [Section 10.2](#). For each subgroup, the hazard ratio for treatment arm will be estimated and the KM plot will be produced. Forest plots will be used to graphically display the hazard ratios and 95% confidence intervals across subgroups. Kaplan-Meier estimates will be provided for each treatment arm within each subgroup.

Survival rate at one-, two-, and three-year after randomization will be estimated for each treatment arm using the Kaplan-Meier product-limit method. Greenwood's formula will be used to calculate the standard error of the Kaplan-Meier estimate and corresponding 95% confidence interval.

To supplement the analysis of OS, a summary of the subsequent anti-cancer therapies and interventions initiated after the discontinuation of study treatment will be provided. Such therapies will be collected during the scheduled post-treatment follow-up assessments.

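### The Hochberg rule for ORR and OS has no direction condition, so after a positive PFS result a significantly adverse OS result can be labelled positive and can let ORR pass at 0.05 instead of 0.025

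*SAP*

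**What the plan says.** SAP 10.1 tests PFS first: "the test will be performed at two-sided 5% significance level". The secondary tests follow "when the primary PFS analysis is positive", using the Hochberg procedure on ORR and OS "to strongly control the type I error at 5% level". Table 2 orders the two P values and rejects by size alone. The text below it restates the table: "ORR and OS will both be considered positive if each analysis yields a P value of" at most 0.05, and if only one P value exceeds 0.05, "the other must yield a P value ≤ 0.025 to be considered positive".

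The tests that supply the P values are in SAP 10.4 and 10.6. For response, "The inferential comparison of the observed ORRs will be made using the Cochran-Mantel-Haenszel Chi-square test", stratified. For survival, the stratified log-rank statistic is used to "test the null hypothesis that the distribution of OS times is equal for the 2 treatment arms". SAP 10.1 states two-sidedness for PFS and for quality of life, but not for ORR or OS. Neither document defines a positive result as one favouring CDX-011, or says what follows if OS is significantly worse.

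**The concern.** A chi-square test and a test of equal survival distributions can both reject when CDX-011 is worse. Because Table 2 looks only at the size of the P values, an adverse OS result has two effects.

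- OS itself can meet the SAP's wording for positive.
- OS can become the small P value that releases ORR at its full 0.05 level. An ORR P value of 0.04 fails beside a neutral OS result and passes beside a significantly harmful one.

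Gains in PFS and response alongside a loss in survival are the case in which a secondary-endpoint rule most needs to be unambiguous. OS is one of only two secondary endpoints that are formally tested.

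**Working it through.** **Plan's own figures.** Hochberg with two independent two-sided P values under the global null gives 1 − (1 − 0.025)² + (0.05 − 0.025)² = 0.0500, which is the stated 5%. Simulated at correlations 0, 0.3, 0.6 and 0.9, the familywise error is 0.050, 0.049, 0.047 and 0.042. The design figure also reproduces: (1.960 + 1.036)² / [(2/9)(ln 0.64)²] = 202.9, so 203 events.

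**The rule applied to cases (PFS positive in each).**

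| ORR (favours CDX-011) | OS | Table 2, read literally |
|---|---|---|
| P = 0.04 | P = 0.03, worse | both positive |
| P = 0.04 | P = 0.50, neutral | neither |
| P = 0.20 | P = 0.04, worse | neither |
| P = 0.20 | P = 0.02, worse | OS positive |

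Rows 1 and 2 show the ORR decision turning on harm. Row 3 shows that a significantly worse OS is not always labelled positive.

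**How often. Inputs.** From the documents: 2:1 allocation, 200 versus 100 (SAP 5). Assumed, because the documents give no values: true OS hazard ratio 1.3 against CDX-011; 100, 120 or 150 deaths; correlation 0 or 0.3 between the ORR and OS statistics, each signed so that positive favours CDX-011; true ORR either equal in the arms or 31% versus 20%. The PFS gate is not applied.

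**OS statistic.** Its mean in the harmful direction is ln(1.3) × √(D × 2/9). For D = 100 this is 0.2624 × 4.714 = 1.237.

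- P ≤ 0.05 and harmful: Φ(1.237 − 1.960) = 0.235.
- P ≤ 0.025 and harmful: Φ(1.237 − 2.241) = 0.158.
- Harmful with P between 0.025 and 0.05: 0.235 − 0.158 = 0.077.

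**ORR statistic.** Under the null, the favourable band 0.025 < P ≤ 0.05 has probability 0.0125, and P ≤ 0.05 in either direction has probability 0.05. At 31% versus 20% the mean is 0.11 / √(0.31 × 0.69/200 + 0.20 × 0.80/100) = 0.11/0.0517 = 2.13. The favourable band then has probability 0.112, and P ≤ 0.05 has probability 0.567.

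**Combined, D = 100, correlation 0.**

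- Harmful OS labelled positive: 0.158 + 0.077 × 0.05 = 0.16 (ORR null); 0.158 + 0.077 × 0.567 = 0.20 (31% versus 20%).
- ORR decision changes: 0.0125 × 0.235 = 0.003 (ORR null); 0.112 × 0.235 = 0.026 (31% versus 20%).

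**All cases, bivariate normal, correlation 0 to 0.3.**

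| Deaths | OS significantly harmful | Labelled positive, ORR null | Labelled positive, ORR 31% v 20% | ORR decision changes, ORR null | ORR decision changes, ORR 31% v 20% |
|---|---|---|---|---|---|
| 100 | 23.5% | 16% | 19–20% | 0.1–0.3% | 2.5–2.6% |
| 120 | 27.3% | 19% | 23–24% | 0.1–0.3% | 3.0% |
| 150 | 32.8% | 24% | 28–29% | 0.2–0.4% | 3.6–3.7% |

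**Limiting case.** If OS is decisively worse and ORR is null, ORR is declared in CDX-011's favour with probability 0.025 under the literal rule and 0.0125 under a directional rule.

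**The case against.** The strongest reply is that a positive result ordinarily means benefit. SAP 10.1 uses the same word for the PFS gate, also without a direction, and nobody would let a harmful PFS result open that gate. SAP 2 presents ORR and OS as measures of anti-cancer activity. Table 2 itself says only reject, which is correct for an equality null. An adverse OS result would also be visible: SAP 10.6 plans Kaplan-Meier curves by arm and one-, two- and three-year survival rates, and Protocol 12.5.1 adds a stratified Cox hazard ratio.

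Much of this stands. It makes it unlikely that harmful survival would be reported as a success. It does not settle whether an adverse OS P value still counts as the P value at or below 0.05 that releases ORR. If one-sided P values were intended the problem would vanish, but the SAP does not say so, and the chi-square test and the equality null point to two-sided tests.

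A reader might infer three stronger things that the documents do not support.

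- *Any significantly worse OS result is called positive.* It is not. PFS must be positive first, and then OS needs P ≤ 0.025, or P ≤ 0.05 with ORR also at P ≤ 0.05.
- *Type I error is inflated.* It is not. Familywise error for the equality nulls stays at or below 5%, and ORR's own level never exceeds 0.05 two-sided, or 0.025 in the favourable direction.
- *The 23.5–32.8% chance of significant OS harm measures the effect on ORR.* It is only the power to detect harm. The ORR decision changes far less often.

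**Conclusion.** The point holds as a fault in a stated decision rule: after a positive PFS result, SAP 10.1 and Table 2 can label harmful survival positive and can make the ORR claim easier because of it. The error rates are intact. Under the assumptions above, and before the PFS gate (which can only lower the figures), harmful OS is labelled positive with probability about 16–29%. The ORR conclusion changes with probability about 0.1–0.4% when ORR is truly null. It changes with probability 2.5–3.7% at 31% versus 20%, an effect close to the threshold, so near the worst case, and there the ORR difference is real. The hazard ratio, death counts, response rates and correlation are all assumed. This is a minor point, unlikely to alter the trial's outcome, but simple to close before the data are unblinded.

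**What to change.** In Table 2 and the text below it, use one-sided P values in favour of CDX-011: both endpoints positive if both are at most 0.025; otherwise the smaller must be at most 0.0125. Equivalently, keep the two-sided thresholds and count any endpoint whose estimate favours capecitabine as P > 0.05. Replace the bare word positive with *considered positive in favour of CDX-011*, and use the same wording for the PFS gate.

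The cost is a few lines in the SAP; the Hochberg rule does not appear in the protocol. Decisions are unchanged whenever both estimates favour CDX-011, so no power is lost when both effects do. The ORR threshold becomes stricter (0.025 instead of 0.05, two-sided) only when OS is significantly adverse, and likewise with the two endpoints exchanged. Under the independent global null, the familywise chance of a false claim of benefit is 1 − (1 − 0.0125)² + 0.0125² = 0.025.
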